6.1 Study design

This protocol describes a multicenter, open label study that will be conducted in the United States of America (US). Approximately 10 sites in the US will participate in this study. Each site should dose between 5 and 15 subjects. No site should dose more than 20 subjects unless prior approval of the sponsor is obtained. The maximum number should in no case exceed 25 subjects.

The clinical study will consist of:

- a screening visit (within 14 days before treatment), at which eligibility of subjects for study participation will be assessed (Visit 1)
- a baseline/treatment visit, at which eligible subjects will receive PDT with application of the content of 3 tubes of BF-200 ALA (Visit 2)
- two interim visits for safety assessment 7 days (\pm 2 days) (Visit 3) and 14 days (\pm 2 days) (Visit 4) post PDT
- a final clinic visit, 28 (\pm 7) days post PDT, at which safety and tolerability assessments will be performed (Visit 5)

[Figure 1](#) illustrates treatment details on study visits. An overview of scheduled assessments is provided in [Table 1](#).

* Visit 2 can be rescheduled once within 14 days after the scheduled date if the dosing day exclusion criterion (sunburn or other possible confounding skin conditions inside or in close proximity (< 10 cm distance) to the treatment field) is met and if the sunburn or other confounding skin conditions is/are expected to resolve within 14 days.

Figure 1: Summary of study visits

The PDT procedure (preparation of treatment field, drug application, incubation, illumination) will be performed similar to the prescribing information of Ameluz® (28). Details will be described in [Section 8](#).

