8.3 Application of BF-200 ALA

[figure not shown]
The treatment field will be localized and documented as described in [Section 6.3](#). A treatment field does not necessarily have to be continuous, but the (discontinuous) treatment field should cover a total area of approximately 60 cm² and must allow illumination in one step (see [Sections 6.3](#) and [8.4](#)).

AK lesions located outside the specified treatment field will not be considered for treatment in this study. For treatment of these AK lesions, subjects will be treated according to standard of care at the discretion of the investigator considering requirements in [Section 9](#). Most preferably, treatment of these lesions should be performed after final assessments at the end of the study (Visit 5). The treatment field should be prepared for IMP application by degreasing (using ethanol or isopropanol), removal of scabs and crusts, and if appropriate roughening of the surface, (e.g. by mild debridement). Care should be taken to avoid bleeding, especially when screened subjects report non-significant acquired or inherited coagulation defects and/or receive treatment with e.g. 81 mg acetylsalicylic acid per day or warfarin.

After this preparation, the content of three tubes of the IMP will be administered to the entire 60 cm² treatment field, covering the skin with a film of approximately 1 mm thickness. All AK target lesions should have a minimal distance of 1 cm to the border of the treatment field. The application will be performed using glove-protected fingertips or a spatula. Care should be taken to avoid that the study medication is applied to the upper and lower eyelids, the lip area (not past the vermillion border) and in the nostrils. In case of accidental contact of study medication with the eyes or mucous membranes, rinsing with water for at least 5 min will be performed.

The IMP will be allowed to dry for approximately 10 min, before a light-blocking, occlusive dressing (e.g. Tegaderm™ dressing plus aluminum foil) will be placed over the treatment field. After the incubation time of $3 \text{ h} \pm 10 \text{ min}$, the light-blocking, occlusive dressing will be removed and the remaining gel should be wiped off.

The incubation time starts when light-blocking, occlusive dressing is placed and ends with removal of the IMP. [Figure 2](#) illustrates the treatment procedure.

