An approximately 3 ml EDTA (ethylenediaminetetraacetic acid) blood sample, and an approximately 7.5 ml serum sample will be collected. The total blood loss for safety laboratory examinations will be approximately 21 ml.

- *Clinical chemistry parameters*

Glucose, creatinine, total bilirubin, aspartate aminotransferase (AST), alanine aminotransferase (ALT), lactate dehydrogenase (LDH), alkaline phosphatase (AP), gamma glutamyl transferase (GGT), potassium, sodium, calcium, total protein, albumin

- *Hematology parameters*

Hemoglobin, hematocrit, red blood cell count, leukocyte count (white blood cells (WBC)) with differential count (neutrophils, lymphocytes, monocytes, eosinophils, basophils), and platelet count.

- **Urine**

An approximately 30 ml urine sample will be collected .The following parameters will be measured:

- *Urinalysis parameters*

Glucose, bilirubin, ketones, specific gravity, blood, pH, protein, urobilinogen, nitrite, leucocytes.

Urinalysis will be performed at the investigational site from a sample of fresh mid-stream urine using a dipstick.

Pregnancy test in females of reproductive potential

A serum pregnancy test (β -human chorionic gonadotropin (β -hCG) test) will be performed at screening (Visit 1) and 28 days after the PDT (Visit 5). At PDT-visit (Visit 2), a urine dipstick pregnancy test will be performed.

Adverse events

During the study, all (S)AEs have to be recorded as outlined in [Section 11](#). If possible, each subject should be assessed by the same investigator/staff personnel throughout the study.

• Application site reactions

The term application site reaction encompasses all reactions occurring in the treatment field after starting PDT treatment and can be subclassified into the more specific categories application site discomfort and application site skin reactions.

• Application site discomfort

At Visit 2, application site discomfort during and after PDT, and at Visit 3 to Visit 5 application site discomfort after PDT will be assessed asking non-leading questions like “Have you noticed anything in the treatment surrounding areas since we last saw you?” Any signs or symptoms reported by the subject that correspond to the application site discomfort categories as outlined below should be assessed as described in [Section 11.1.1](#).

Application site discomfort categories are for example:

- Burning
- Hyperesthesia
- Pain
- Paraesthesia
- Pruritus
- Stinging
- Warmth
- Other

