11.2 Period of AE collection

Collection of AEs starts with signing the informed consent documents until the end of the study. AEs will be discriminated as pre-treatment adverse events (PTAEs) and TEAEs.

- AEs developing between signing the ICF and IMP application at Visit 2 will be considered as PTAEs and documented as an AE.
- TEAEs are defined as all AEs or SAEs with onset or worsening after treatment with IMP up to Visit 5
- If the investigator detects an SAE in a subject after end of study, and considers the event possibly related to prior study treatment or procedures, he/she should report this event to the pharmacovigilance department of the sponsor (see [Section 11.3.1](#)).

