#### 3.2 Safety Analysis Set (SAF)

The safety analysis set (SAF) will include all subjects who undergo at least one of the following treatment procedures: preparation of the treatment field, application of BF-200 ALA, or illumination. If it is not certain whether a subject has received any of the treatment procedures, the subject will be included in the SAF.

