## 4.4 Analysis of Endpoints

### 4.4.1 Adverse Events

AEs will be coded by using the Medical dictionary for regulatory activities (MedDRA, MedDRA version available at the day of database closure). If an AE occurs in multiple treatment areas, it is reported separately for each treatment area within the eCRF. Thus, some AEs are counted repeatedly for the analysis.

Analysis will focus on severity and duration of TEAEs. TEAEs are defined as all AEs with onset or worsening after treatment with IMP up to Visit 5 (Final visit). AEs with start on the day of PDT which are unrelated or unlikely related to IMP belonging to AE category 'NEW LESION' and with action taken 'PDT treatment' will be classified as pre-treatment emergent adverse events. If unclear due to incomplete start date/time of AE or IMP application or uncertainty about worsening of AE, AEs will be assumed as TEAEs. AEs developing between signing the ICF and IMP application at Visit 2 will be considered as pre-treatment adverse events (PTAEs). TEAEs as defined above, will be tabulated by system organ class (SOC) and preferred term (PT) (MedDRA). The number of entries, as well as the number and rate of affected subjects will be reported for each treatment area and overall.

TEAEs will also be tabulated by relationship to IMP and/or medical device and by worst severity. TEAEs are considered being related to IMP or medical device, if causal relationship between IMP or medical device and the TEAE is at least possible or relationship assessment is missing. For AEs with changes in severity, the worst severity per AE and subject will be tabulated.

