#### Duration and severity of adverse events

Duration of TEAEs by severity will be presented for related PTs which occurred in at least 2 subjects. For all those TEAEs (related to IMP and/or medical device), the duration of the AEs will be tabulated by severity. For each of these TEAEs, the mean duration of each severity category, based on all subjects who experienced these TEAEs, will be presented in a stacked bar chart. The proportion of days in the different severity categories as a percentage of the total duration will be presented in a frequency table for each TEAE. For the frequency table and the stacked bar charts, the calculations for each severity category will be performed with reference to all subjects who experienced this TEAE, regardless of severity. If a severity category does not occur in a subject, the duration in this category is set to 0. Calculation of duration of severity will only be done for AEs with complete start and stop dates. AEs with incomplete start or stop dates or ongoing AEs will not be considered for this analysis.

If for a TEAE only one severity is recorded during the day, then the duration of the severity of this TEAE will be set to one day. If severity changes during the day, more than one change can be recorded. For the calculation of the duration of each severity category on this day, the day will be

divided by number of changes during the day (so that duration can be e.g. 0.5 day, 0.33 day). Note that on day 1 only one severity is recorded.

Listing will include the start day of TEAEs after PDT. Calculation of TEAE start after PDT is performed in days as follows: start date of TEAE- start date of PDT.

PTAEs will be listed separately and not included in any tables or other listings.

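### Application site reactions count from the start of PDT, which includes field preparation, but a clearly timed, non-worsening reaction to preparation is classed as pre-treatment and left out of the endpoint tables

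*SAP*

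**What the plan says.** **Start point of the endpoint.** Protocol 10.2.7: "The term application site reaction encompasses all reactions occurring in the treatment field after starting PDT treatment". Protocol 6.1 lists what PDT consists of: "The PDT procedure (preparation of treatment field, drug application, incubation, illumination". Protocol 8.3 describes preparation, before any gel is applied, as degreasing with alcohol, "removal of scabs and crusts, and if appropriate roughening of the surface, (e.g. by mild debridement"). Both documents treat preparation as a treatment procedure: any one of "preparation of the treatment field, application of BF-200 ALA, or illumination" puts a subject in the safety analysis set (SAP 3.2; Protocol 14.3 agrees).

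**Start point of the analysis.** Protocol 11.2: "AEs developing between signing the ICF and IMP application at Visit 2 will be considered as PTAEs and documented as an AE". SAP 4.4.1 repeats the rule: "AEs developing between signing the ICF and IMP application at Visit 2 will be considered as pre-treatment adverse events (PTAEs". The other side of the cut-off is: "TEAEs are defined as all AEs with onset or worsening after treatment with IMP up to Visit 5". SAP 4.4.1 adds that incomplete times, or uncertainty about worsening, resolve to TEAE.

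**Reporting.** SAP 4.4.1, under duration and severity: "PTAEs will be listed separately and not included in any tables or other listings". The application site reaction table in the same section gives the number and proportion of subjects with skin reactions and discomfort. SAP 4.4.3 lists the details of both.

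**The concern.** The same endpoint has two start points. The protocol's definition opens when preparation begins. The analysis opens when the gel goes on. A reaction that falls between them is an endpoint event by definition and a pre-treatment event by analysis rule, and the SAP gives pre-treatment events no table.

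The study is single-arm and descriptive, so its safety tables are its result. Its objective is the safety of the whole PDT procedure over about 60 cm², not of the gel alone. Protocol 11.1.1 names the effect of an invasive procedure required by the protocol as an example of an AE. Leaving such events out can only lower the counts for terms such as erosion or stinging, which favours the product. The SAP already has a special day-of-PDT rule for new lesions, but none for preparation reactions.

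**Working it through.** The documents give no figure on this point and no sample size calculation, so there is nothing to reproduce. The check is a trace of the rules, followed by an illustration of size.

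**Trace.** Take a treated subject with an erosion from debridement, a recorded onset before the gel, and no later worsening.

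| Question | Source | Answer |
|---|---|---|
| Is it in the treatment field after PDT started? | Protocol 10.2.7, 6.1 | Yes, so it is an application site reaction |
| Can its timing be established? | Protocol 11.3 collects AE start date and time; Protocol 8.3 records the gel start time | Yes, if recorded |
| Is onset before IMP application? | Protocol 11.2, SAP 4.4.1 | Yes, so PTAE |
| Does the worsening or uncertainty rule apply? | SAP 4.4.1 | No, by construction |
| Does it enter the application site table or the SAP 4.4.3 listings? | SAP 4.4.1, bar on PTAEs | No; PTAE listing only |

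**Size.** Inputs: N = about 100 (Protocol 7.1, SAP 1.3). The documents do not give p, the share of subjects with a pre-gel onset reaction, or w, the share of those that become TEAEs through worsening or uncertainty. Both are assumed, with one event per affected subject.

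- Expected number tabulated = N × p × w
- Expected number in the PTAE listing only = N × p × (1 − w)
- Probability that at least one is tabulated = 1 − (1 − w)^(N × p)

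| p | w | Tabulated | PTAE listing only | P(at least one tabulated) |
|---|---|---|---|---|
| 5% | 0 | 0 | 5 | 0 |
| 5% | 10% | 0.5 | 4.5 | 0.41 |
| 5% | 50% | 2.5 | 2.5 | 0.97 |
| 10% | 0 | 0 | 10 | 0 |
| 10% | 10% | 1.0 | 9.0 | 0.65 |
| 10% | 50% | 5.0 | 5.0 | 0.999 |
| 25% | 10% | 2.5 | 22.5 | 0.93 |
| 25% | 50% | 12.5 | 12.5 | about 1 |

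For example, with p = 10% and w = 10%: 100 × 0.10 × 0.10 = 1.0 tabulated, 100 × 0.10 × 0.90 = 9.0 listed only, and 1 − 0.9^10 = 0.65.

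**Any-reaction rate.** Protocol 4.3 reports application site reactions in 84-100% of subjects in earlier trials. A subject is missed at this level only if the preparation reaction is the sole one, so at most 100 × (1 − 0.84) = 16 and at least 100 × (1 − 1.00) = 0 subjects could be affected. If preparation reactions are independent of the others (an assumption) and w = 0, the expected number missed at the 84% end is 100 × p × 0.16. That is 0.8 for p = 5%, 1.6 for p = 10% and 4.0 for p = 25%.

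**The case against.** The best defence is that few preparation reactions will meet the conditions for exclusion.

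- Protocol 10.1.2 schedules reaction assessments within 10 minutes and at 60 minutes after illumination, with none between preparation and gel. Protocol 11.3 asks only for the maximum severity on an event's first day. Worsening between preparation and illumination may therefore be unknowable, and SAP 4.4.1 sends uncertainty about worsening to TEAE. This narrows the gap without closing it. Protocol 10.2.7 also asks for evaluation during PDT, start times are collected, and the SAP does not say whether a single day-1 severity counts as uncertainty.
- The cut-off is in the protocol too, and a TEAE tied to the IMP is conventional. That stands: the SAP did not invent the rule, and the TEAE definition need not change. What the SAP adds is the bar from tables.
- The events stay visible in the PTAE listing, and bleeding in the application area is its own eCRF item (Protocol 8.3). Both are true. But a listing yields no rate, and SAP 4.3 names no bleeding summary, although Protocol 14.4.1 promises tabulated procedure details.
- The application site table is not worded as TEAE-only, and the overview table has a row for all AEs. This shows that the SAP is at odds with itself, because the bar covers any table. The table specifications are in SAP Appendix A, which is not among the documents reviewed.

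A reader might infer that debridement reactions are counted as zero in every treated subject. The documents do not support that: it needs w = 0, and only subjects who have such a reaction are affected. A reader might also infer that the reported durations are too short. That is not shown either. The duration tables cover only TEAEs related to the IMP or device, so a preparation reaction's place there depends on the causality call as well as on its timing.

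**Conclusion.** The point holds in a limited form. A preparation reaction with a clear pre-gel onset and no later worsening meets the protocol's definition of an application site reaction but, on the SAP's wording, appears only in the PTAE listing. The error runs in the favourable direction and falls on individual terms.

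Its size cannot be derived from the documents. Under the assumed p it ranges from none (w = 1) to all such reactions (w = 0), for example 0 to 10 of about 100 subjects at p = 10%. The any-reaction rate would change little. The conclusion rests on reading the bar on PTAEs literally and on taking field preparation as the start of PDT, as Protocol 6.1 does. It is worth correcting before analysis because the passages conflict and the correction is small.

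**What to change.** Amend SAP 4.4.1 in two places and leave the TEAE definition tied to the IMP.

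1. After the sentence on PTAE listings, add: *AEs of category application site skin reaction or application site discomfort with onset on the day of PDT are exempt from this restriction. They are included in the application site reaction table and in the listings of section 4.4.3. Those with onset before IMP application are shown in a separate, flagged row.*
2. After the rule on unclear cases, add: *Where worsening on the day of PDT cannot be determined because only the maximum severity is recorded for that day, the event falls under uncertainty about worsening and is classified as a TEAE.*

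The exemption needs the AE category, the AE start date and time, the PDT date and the gel start time, all of which the protocol already collects. It does not need a preparation start time, which is not among the procedure items listed for the eCRF in Protocol 8.3. The flagged row keeps preparation reactions apart from those of gel and light.

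The cost is a little extra programming, a row in the table specification, and slightly higher rates for some terms. The general TEAE tables by system organ class and preferred term keep their cut-off at the gel. They change only where the second sentence resolves an unclear case.

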#### Frequency of adverse events

An overview table showing the number of entries, as well as the number and rate of affected subjects with AEs, SAEs, TEAEs, serious TEAEs, TEAEs leading to death, TEAEs related to IMP, TEAEs related to medical device, TEAEs leading to study discontinuation, and TEAEs related to IMP or medical device will be shown.

TEAEs leading to death, serious TEAEs, TEAEs related to IMP, and TEAEs related to medical device will be presented separately.

#### Subgroup analysis

Additionally, TEAEs will be tabulated by age groups ( $\geq 18 - \leq 65$  /  $\geq 66 - \leq 74$  /  $\geq 75$ ), sex (male / female) and skin type subgroups (Type I-III, Type IV-VI).

A stratified analysis of related TEAEs will be done for subjects with major PDs as classified during DRM and subjects without major PDs.

#### Duration and severity of adverse events

Duration of TEAEs by severity will be presented for related PTs which occurred in at least 2 subjects. For all those TEAEs (related to IMP and/or medical device), the duration of the AEs will be tabulated by severity. For each of these TEAEs, the mean duration of each severity category, based on all subjects who experienced these TEAEs, will be presented in a stacked bar chart. The proportion of days in the different severity categories as a percentage of the total duration will be presented in a frequency table for each TEAE. For the frequency table and the stacked bar charts, the calculations for each severity category will be performed with reference to all subjects who experienced this TEAE, regardless of severity. If a severity category does not occur in a subject, the duration in this category is set to 0. Calculation of duration of severity will only be done for AEs with complete start and stop dates. AEs with incomplete start or stop dates or ongoing AEs will not be considered for this analysis.

If for a TEAE only one severity is recorded during the day, then the duration of the severity of this TEAE will be set to one day. If severity changes during the day, more than one change can be recorded. For the calculation of the duration of each severity category on this day, the day will be

divided by number of changes during the day (so that duration can be e.g. 0.5 day, 0.33 day). Note that on day 1 only one severity is recorded.

Listing will include the start day of TEAEs after PDT. Calculation of TEAE start after PDT is performed in days as follows: start date of TEAE- start date of PDT.

PTAEs will be listed separately and not included in any tables or other listings.

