14.4.3 Evaluation of the Safety Endpoints

Safety analyses

All safety endpoints will be analyzed descriptively and in an exploratory way. These safety analyses will be performed for the safety set. Selected safety analyses will be conducted overall and stratified by age groups, sex, skin type, and treatment area.

AEs will be coded according to the latest Medical Dictionary for Regulatory Activities (MedDRA) version available at the day of database closure. The analysis will focus on the TEAEs. TEAEs will be summarized and tabulated according to primary system organ class and preferred term. TEAEs leading to death and TEAEs resulting in discontinuation of study will be tabulated using frequency tables.

The mean total duration of TEAEs including the breakdown of severity category (mild, moderate, severe) will be presented overall and by treatment area.

A listing of subjects with AEs will be provided for all subjects in the SAF.

The frequency of application site skin reactions and of application site discomfort will be presented overall, and per treatment area. The mean pain score (NRS-11) and the respective confidence intervals (CIs), and the range will be presented overall and by treatment area.

All laboratory values will be classified as normal or abnormal according to the laboratory's normal ranges and indicated as clinically significant or non-clinically significant by the investigator. Frequency tables for clinically significant findings will be provided. Laboratory values that are out of range and considered clinically significant will be additionally documented in the medical history (Visit 1) or as AEs (28 days after the PDT, Visit 5) and listed as such.

The analyses of variables for vital signs will focus on

- A) the evaluation of the change from baseline (Visit 2, first measurement after the subject arrived at the site) to values on subsequent clinical visits and
- B) The evaluation of the change on Visit 2 from baseline (first measurement after the subject arrived at the site) to values obtained prior and after illumination (until 60 min post illumination).

Descriptive analysis (number of subjects, mean, median and SD, minimum, maximum) of the time course and of changes from baseline to post baseline time points will be presented.

Physical examinations will include the following body systems: head, neck, skin, lymph nodes, thorax including heart and lung, abdomen, and musculoskeletal, peripheral vascular and nervous system.

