## 2 Endpoints

The endpoints of the study are:

- Frequency and severity of adverse events (AEs), serious AEs (SAEs), and treatment-emergent adverse events (TEAEs). TEAEs are defined as all AEs with onset or worsening after treatment with IMP up to Visit 5
- Duration of TEAEs including the breakdown of severity category (mild, moderate, severe)
- Assessment of new lesions (AK, non-melanoma skin cancer (NMSC) such as basal cell carcinoma (BCC), squamous cell carcinoma (SCC) or Bowens disease and melanoma) if they occur inside the treatment field
- Assessment of new lesions (AK, NMSC such as BCC, SCC or Bowens disease and melanoma) if they occur around the treatment field at a distance of < 10 cm
- Application site skin reactions during and post PDT, assessed by the investigator
- Application site discomfort during and post PDT, reported by the subjects
- Application site pain during illumination, as assessed by the subjects using an 11-point numeric rating scale
- Changes in vital signs
- Safety laboratory data
- Physical examination data
- Neurological assessments

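### The SAP's only duration analysis is limited to related preferred terms seen in at least 2 subjects, although the protocol and the SAP's own endpoint list set the duration endpoint for all TEAEs

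*SAP*

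**What the plan says.** Protocol sections 5.1 and 14.2 list the duration of TEAEs by severity category as an endpoint. Section 14.4.3 states the analysis: "The mean total duration of TEAEs including the breakdown of severity category (mild, moderate, severe) will be presented overall and by treatment area". Protocol 11.2 gives the scope of the term: "TEAEs are defined as all AEs or SAEs with onset or worsening after treatment with IMP up to Visit 5". Causality plays no part in that definition.

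SAP section 2 repeats the endpoint without a restriction, and the opening of SAP 4.4.1 names severity and duration of TEAEs as the focus of the analysis. The subsection on duration and severity then narrows it: "Duration of TEAEs by severity will be presented for related PTs which occurred in at least 2 subjects". The next sentence carries the causality condition into the table: "For all those TEAEs (related to IMP and/or medical device), the duration of the AEs will be tabulated by severity". The stacked bar chart and the table of percentages of days are built on the same set of events.

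SAP 4.4.1 counts a TEAE as related if the causal relationship to IMP or device "is at least possible or relationship assessment is missing".

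**The concern.** The analysis does not deliver the endpoint as both documents define it. Two filters have been added. One depends on the investigator's causality rating in a single-arm, open-label study, where no comparator group is available to check that rating. The other depends on how many subjects happen to show the same PT.

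The supplied SAP text neither explains the filters nor marks them as a change from protocol 14.4.3. Protocol 14.1 leaves technical details to the SAP, but deciding which events count toward a named endpoint goes beyond a technical detail.

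Duration is a live question for this treatment. Protocol 4.3 reports that symptoms usually lasted 1 to 4 days but in some cases lasted 1 to 2 weeks or longer. The SAP's tables for application site reactions and for adverse events of special interest are described in terms of frequency or intensity, not duration, so they do not fill the gap.

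**Working it through.** The documents give no sample size calculation, alpha or power for this point, so there is no figure to reproduce. The check is a comparison of texts, followed by an illustration of the 2-subject threshold.

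**Step 1: scope of the endpoint against scope of the analysis**

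| Place | Events covered | Causality condition | Frequency condition |
|---|---|---|---|
| Protocol 5.1, 14.2, 14.4.3 | TEAEs | none | none |
| Protocol 11.2 (definition) | all AEs after IMP up to Visit 5 | none | none |
| SAP 2 | TEAEs | none | none |
| SAP 4.4.1, duration and severity | PTs of related TEAEs | at least possible, or missing | at least 2 subjects |

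Two groups fall outside the last row: TEAEs rated unrelated or unlikely related, and related PTs seen in one subject only.

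The wording also leaves two things open: whether each of the 2 subjects needs a related event, and whether they are counted overall or within each treatment area.

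**Step 2: how often the threshold bites**

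Inputs: n = 100 (SAP 1.3, about 100 subjects). The documents give no PT-level rates, so the true per-subject rate p of a related PT is assumed over a range. The 2 subjects are counted overall, and subjects are treated as independent.

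- Not seen: P0 = (1 − p)^n
- Seen in exactly one subject: P1 = n·p·(1 − p)^(n − 1)
- Reaches the threshold: P(≥2) = 1 − P0 − P1
- Share of observed PTs that fall below the threshold: P1 / (1 − P0)

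At p = 1%, P0 = 0.99^100 = 0.366 and P1 = 100 × 0.01 × 0.99^99 = 0.370. So P(≥2) = 1 − 0.366 − 0.370 = 0.264, and the share is 0.370 / 0.634 = 0.583.

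| Assumed true rate | Exactly 1 subject | At least 2 subjects | If seen at all, seen in only one |
|---|---|---|---|
| 0.5% | 30% | 9% | 77% |
| 1% | 37% | 26% | 58% |
| 2% | 27% | 60% | 31% |
| 3% | 15% | 81% | 15% |
| 5% | 3% | 96% | 3% |

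Solving P(≥2) = 0.80 gives a true rate of about 3.0%; solving for 0.95 gives about 4.7%. With 90 subjects instead of 100, the chance of reaching 2 subjects is 23% at 1%, 54% at 2% and 94% at 5%, so the picture does not depend on the exact number treated.

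No comparable figure can be given for the causality filter, because the documents do not say what share of TEAEs is expected to be rated unrelated or unlikely related.

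**The case against.** The case for leaving the plan alone has several parts.

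- **The events are not hidden.** A reader might infer that they vanish from the results. The documents do not support that. All TEAEs are tabulated by system organ class and PT, and by relationship and worst severity (SAP 4.4.1). Protocol 14.4.3 adds: "A listing of subjects with AEs will be provided for all subjects in the SAF". Protocol 11.3 requires start and stop dates and dates of severity change. This stands: only the duration summary is missing. A listing is still not the summary that protocol 14.4.3 describes.
- **A mean over one subject is that subject's value.** It can be read from the listed dates, so leaving out such rows is largely a matter of presentation. This mostly stands for the threshold. It does not touch the causality filter, which can remove events seen in several subjects.
- **Related is defined broadly.** Only events rated unrelated or unlikely related fall out, so common application site reactions will probably be kept. This stands and limits the size of the problem.
- **The rate of loss is easily overstated.** The exact 95% interval for 1 of 100 is 0.03 to 5.4%, and a reader might infer that events with true rates up to about 5% are likely to be left out. They are not: at 5% a PT misses the threshold only about 3.7% of the time (1 − 0.963).
- **Display by area is already planned.** A reader might also infer that overall and by-area results are missing. SAP section 4 sets both for all analyses unless stated otherwise. The gap concerns which TEAEs enter.
- **Another rule bears more directly on long-lasting reactions.** In the same subsection, "AEs with incomplete start or stop dates or ongoing AEs will not be considered for this analysis". That is correct, and removing the two filters would not bring those events in. It is a separate matter.
- **Appendix A might hold more.** It describes the tables in detail and is not in the supplied text, so an additional duration table there cannot be excluded.

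Finally, all analyses are exploratory, and the SAP states that it was finalized before the first subject was enrolled, so on its face the restriction was not chosen from the data. Both points lower the stakes but do not reconcile the texts.

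**Conclusion.** The mismatch is real and minor. As the supplied text stands, following the SAP does not deliver the duration endpoint that protocol 14.4.3 and SAP section 2 set. TEAEs rated unrelated or unlikely related, and PTs seen in one subject, have no duration summary. They remain in the frequency tables and listings.

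The threshold mainly affects PTs with true rates of roughly 0.5 to 3%. These figures rest on assumed rates, about 100 treated subjects, and counting the 2 subjects overall; counting within treatment areas would exclude more. The effect of the causality filter cannot be sized from the documents. No formal hypothesis depends on this display, and the conclusion is limited to the supplied text, without Appendix A.

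**What to change.** In SAP 4.4.1, under duration and severity of adverse events:

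- Tabulate duration by severity for all TEAEs by PT, using the overall and by-treatment-area display that SAP section 4 already sets.
- Give related TEAEs as a second table.
- Apply the 2-subject threshold only to the stacked bar charts, and state whether it counts subjects overall or within each area, and whether each needs a related event.

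If the sponsor prefers to keep the restriction, the SAP should state it as a change from protocol 14.4.3 and give the reason.

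The cost is a wording change and a longer table in which some rows rest on one subject. No new data are needed, since Protocol 11.3 already requires dates and severity changes for every adverse event.
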